- Observing the participant
- Questioning the participant which should be done in an objective manner
- Receiving an unsolicited complaint from the participant.

Exacerbations of asthma are ordinary, anticipated complications of asthma observed in patients receiving standard of care. Asthma exacerbations requiring hospitalization for 5 or more days or intensive care admission will be considered serious adverse events. For reporting purposes, the date of onset of the exacerbations will be the date of hospital admission and the date of resolution will be the discharge date.

Grading and Relationship Assignment

Adverse events will be recorded and graded 1 to 5 according to the general grade definition below:

Grade 1 Mild - Transient or mild discomforts, no or minimal medical Intervention therapy required, hospitalization not necessary (nonprescription or single use prescription therapy may be employed to relieve symptoms, e.g. acetaminophen or ibuprofen).

Grade 2 Moderate - Mild to moderate limitation in activity; some assistance may be needed, no or minimal intervention/therapy required, hospitalization possible

Grade 3 Severe - Marked limitation in activity, some assistance usually required; medical intervention/therapy required, hospitalization possible.

Grade 4 Life-threatening - Extreme limitation in activity, significant assistance required; significant medical therapy intervention required, hospitalization or hospice care probable.

Grade 5 Death

The relationship to study procedures will also be recorded. Adverse events will be assessed as definitely related, probably related, or possibly related, or not related.

An adverse event is considered related to the study procedures if there is a reasonable possibility that the adverse event may have been caused by the procedure.

1. Definitely related: An adverse event that follows a temporal sequence from administration of the procedure; follows a known response pattern to the procedure; is confirmed by improvement after stopping the procedure, and cannot be reasonably explained by a known characteristic of the participant's clinical state or by other therapies or interventions.

2. Probably related: An adverse event that follows a reasonable temporal sequence from administration of the procedure, is confirmed by improvement after stopping the procedure, and cannot be reasonable explained by the known characteristics of the participant's clinical state or other therapies.

3. Possibly related: An adverse event that follows a reasonable temporal sequence from administration of the procedure and follows a known response pattern to the procedure, but could have been produced by the participant's clinical state or by other therapies.

4. Unlikely: An adverse event whose temporal relationship to the study procedures makes a causal relationship improbable and in which other interventions or underlying disease provides plausible explanations.

5. Not related: An adverse event that does not follow a reasonable temporal sequence after administration of the procedure and most likely is explained by the participant's clinical disease state or other therapies.

AE Event Reporting and Management

An Adverse Event Form will be used for reporting all adverse events. An additional form will be required for serious adverse events to collect additional information. Information that will be documented includes a brief description of the event, onset and duration of the event, severity grade of the event, resolution status of the event, and relatedness to the study procedures. Any medical intervention will also be documented.

SAE forms will be faxed to the CDC to the attention of the PI. SAEs will be reported to the CDC by the Study Coordinator and Site Investigator either within 24 hours or within 5-7 days as indicated below:

1. SAEs that do not include a death or life-threatening event will be reported within 5 to 7 days to the CDC.
2. Any death or life-threatening SAE (Grade 4 or 5 SAE) must be reported to the CDC within 24 hours. The PI of the CDC will be notified by email. The site's IRB must also be notified within 24 hours of the site's awareness of the event.
3. The following attributes must be assigned:
 - a. Description
 - b. Date of onset and resolution (if known when initially reported)
 - c. Severity
 - d. Assessment of relatedness to the study procedures
 - e. Action taken

The study site PI (or project coordinator) will notify the CDC IRB of SAEs within 7-10 days. Adverse event reports will be generated by CDC on an ongoing basis and included in annual reports to the CDC IRB.

Study Discontinuation

The study site investigator along with the CDC PI will apply judgment to determine whether an adverse event is of sufficient severity to require that the subject be removed from the study. If necessary, an investigator must suspend any study procedures and institute the necessary medical therapy to protect a subject from any immediate danger.

Subsequent review by the study site PI, IRB, and CDC may suspend further study activities at the site. The CDC and CDC IRB retain the authority to suspend additional enrollment and treatments for the entire study as applicable.

Source documents and Access to Source Data/Documents

The following types of data will be collected: environmental laboratory data (allergens, mold, VOCs, pesticides, PM), clinical laboratory data (urinary pesticide and VOC biomarkers, IgE levels, PCR analysis of acute respiratory illnesses), clinical data (lung function, exhaled nitric oxide, symptom report, health care utilization, medication usage).

Each participating site will maintain appropriate medical and research records for this trial, in compliance with good clinical practices (GCP), regulatory and institutional requirements for the protection of confidentiality of participants. Study staff and investigators and site IRBs may access the records. As part of participating in a CDC-affiliated study, each site will permit authorized representatives of the sponsor, CDC, and regulatory agencies to examine (and when required by applicable law, to copy) de-identified clinical records for the purposes of quality assurance reviews, audits, and evaluation of the study safety and progress.

Timing/Reports

No formal interim analyses are planned. Adverse events and enrollment will be reviewed on an ongoing basis by the PI and the IRBS at CDC and each participating institution. Adverse events and enrollment reports will be generated annually for IRB review.

Study Records Retention

Study documents must be maintained at the research center or a local storage facility for at least five years following the completion of the study. Study documents that must be retained include all participant-related forms, laboratory reports, IRB approval documentation and related correspondence and signed informed consent/assent forms.

V. LIMITATIONS

Generalizability

Geographic location

The proposed study will be conducted in HUD-sponsored housing primarily in urban environments. The majority of HUD properties that participate in the HUD's housing subsidy programs are located in the eastern part of the U.S., thus the geographical distribution of properties available for study is not uniform. In addition, participation in the study is voluntary and before residents can be approached about participation, owners and property managers of the prospective properties must first give consent. As such, our study sample will not be random, which is likely to have implications for the generalizability of our findings.

Socioeconomic status (SES)

The proposed study will be conducted solely in Section 8 housing—thus our study will assess the impact of green housing on the health outcomes of low-income residents. As a result, it may not be appropriate to generalize our findings to children in families with higher socioeconomic status. Also, race (which can be intertwined with SES) could also influence health outcomes either due to genetic susceptibility (K. C. Barnes, 2006) or other unmeasured factors (Drake, Galanter, & Burchard, 2008).

V. SUMMARY OF STRENGTHS

This study is uniquely poised to evaluate relationships between green housing and human health. The nationwide multi-site design will provide contextual information to understand which green building rehabilitation practices are associated with health not only regionally, but nationally. This elucidation then could inform policy about which green components should be implemented without regard to locality, and which components should be modified under certain circumstances (e.g, region or housing type).

The other main strengths of this study are the repeated exposure measurements and the choice of health outcomes (asthma). A cross-sectional design could easily miss the biologically relevant exposures associated with health. By collecting repeated measures of pesticides, VOCs, fungi, and indoor allergens, asthmatic children in both the green and control housing units can be compared prospectively and selection bias will also be minimized. Focusing on sensitive populations such as children with asthma, will give the study the best chance to see relationships between green housing and health, given that those relationships exist.

VII. REFERENCES

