Sample size overviews: The most complete data to obtain sample size estimates for our proposed study are derived primarily from studies of allergens and asthma. Based upon our calculations, we estimate that we will need at least 13 green buildings and 13 control buildings with at least 25 apartments in each building for a total $n = 650$ to detect differences in environmental exposures (notably allergens). In addition, we need at least 548 asthmatic children ($n=274$ in green and $n= 274$ in control buildings) to detect differences in asthma symptom days. With an anticipated loss to follow-up over a 1-year period = 20%, we will need at least 688 children with asthma (7-12 years) and 814 homes to assess exposure differences. We will enroll the children from 832 homes in order to ensure adequate power to detect both the asthma and exposure outcomes for the 13 study sites (i.e., 64 homes in each study site). The details of our sample size calculations are listed below and the equations that were used were from a book on longitudinal data analysis by Diggle, Liang, and Zeger (1994).

Sample size calculations for the overall difference between environmental exposures in green vs. control homes can be given as a simple test of two proportions and means; however a specific difficulty arises when trying to adjust for temporal and spatial correlations between measurements. A study that had enough measurements to assess spatial and temporal correlation was an integrated pest management (IPM) study conducted in New York

City (Chew et al. 2006; Kass et al. 2009). We have used the design effect from this study to estimate the number of clusters (or buildings) needed to detect differences in cockroach allergen because IPM is also one of the main green characteristics in the Green Housing Study. Assumptions from the aforementioned study comparing IPM to non-IPM homes are listed below:

- 1 13 buildings
 - 2 About half were treatment and the other half control
 - 3 3 repeated measures at: baseline (before IPM), 3months later (post-IPM), and 6months later (post-IPM)
 - 4 On average, 25 apartments within each building were measured
 - 5 For the control homes, the correlations between baseline and 3-month follow-up cockroach allergen measurements and 3-month and 6 months follow-up measurements were approximately equal to 0.5.
- Design effect due to clustering = 3.62

Equation 1. Sample size for repeated measures – cockroach allergen.

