Odds ratios (OR) or Rate Ratios (RR) for exposures to environmental agents and cumulative incidence of wheeze and/or other asthma-related morbidity measurements (among children ages 7-12 with asthma).

Odds ratios (OR) or Rate Ratios (RR) for exposures to environmental agents and cumulative incidence of wheeze and/or other asthma-related morbidity measurements (among mothers/ primary caregivers).

This analysis is also secondary; we expect that asthma among adults will be influenced by other factors unrelated to green housing (e.g., their own smoking habits, occupational exposures).

Missing data (e.g. loss to follow-up)

We anticipate the inevitable occurrence of missing data, including dropouts. First, if the missingness of the data is sufficiently small and the associations of interest are sufficiently large, the simple device of imputing upper and lower bound data, if possible, will suffice. That is, a small amount of missing data and a large effect size will allow a unique inference to stand no matter whether the missing data are imputed at their minimum or maximum possible values and used as such. This is consistent with the most conservative approaches adopted in clinical trials wherein subjects lost to follow-up are assumed to have died or to have otherwise suffered the worst possible endpoint. In general however, we must anticipate that we may be facing larger missingness and/or smaller effect sizes and/or impractical upper and lower bounds, such that primary inference changes

between the extremes. In this case we will use the multiple imputation procedure of Rubin (Rubin, 1985) to address the problem. In this technique, a fair amount of effort is devoted to the construction of an imputation model or set of models to provide best estimates of missing endpoints. These best estimates may include the best case or worst case scenarios; the point is that they should most fairly represent data that are missing given the observable information at hand. The imputation models may need to assume data missing at random or they may need further specification to allow for non-ignorable missingness. Each analysis must develop its own best imputation model for missing data, using available observed covariates and non-missing endpoints.

Database management system

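### The minimum/maximum fill that decides whether multiple imputation is used does not bound a green-versus-control difference, so it can pass a result that is not robust

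*Protocol*

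**What the plan says.** The subsection on missing data, under Statistical Analysis and Related Issues in the protocol, sets out a two-step rule.

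- **Step 1.** A simple bounding device is enough "if the missingness of the data is sufficiently small and the associations of interest are sufficiently large". The test is whether a single inference holds "no matter whether the missing data are imputed at their minimum or maximum possible values and used as such". The section presents this as in line with the most conservative practice in clinical trials, "wherein subjects lost to follow-up are assumed to have died or to have otherwise suffered the worst possible endpoint".
- **Step 2.** The section then says that larger missingness, smaller effects or impractical bounds must be expected in general, so that the primary inference may change between the extremes. "In this case we will use the multiple imputation procedure".

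No threshold is given for small missingness or for a large association. Nothing says that the two arms are filled at opposite extremes. The sample size overview in the same part of the protocol anticipates 20% loss over one year, and on that basis "we will need at least 688 children with asthma (7-12 years) and 814 homes".

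**The concern.** The bounding check decides whether multiple imputation is done at all, so it has to be a real bound. The quantity of interest is the contrast between green and control homes. For a contrast, the least favourable case is green dropouts at the worst value with control dropouts at the best, and the most favourable case is the reverse. Giving all dropouts one common value is conservative for a single proportion or mean. It is not conservative for a difference between arms, because the common value largely cancels.

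If the check passes wrongly, an asthma result is reported as unaffected by missing data when it could have vanished or reversed. The filled constants are then analysed as if observed, so the standard errors carry no imputation uncertainty. The choice of method also depends on the outcome result. The comparison is not randomised, so dropout related to both housing type and outcome is a realistic worry.

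**Working it through.** **Inputs**

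- Exit rates of urgent health service use: 8.4% (high-intensity, taken here as green) and 16.4% (low-intensity, taken as control). They come from the Seattle public housing study cited in the sample size section. d = 8.4 - 16.4 = -8.0 points.
- Size: 274 per group for asthma outcomes. With 20% loss, 274/0.80 = 342.5, so 343 per arm. The protocol's 688 in total is 344 per arm, so its figure is reproduced to within one child per arm. Enrolment of 832 homes gives 416 per arm.
- Design effect for asthma outcomes: 1.2.
- Loss L: the protocol anticipates 20%. The 10% case is an assumption, used because the rule is meant for smaller missingness. Equal loss in the two arms is also assumed.
- Test: two-proportion z test with pooled variance multiplied by the design effect, two-sided 0.05.

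**Formulae for a 0/1 outcome with equal loss**

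- All missing at 0: (1-L)p_G - (1-L)p_C = (1-L)d
- All missing at 1: [(1-L)p_G + L] - [(1-L)p_C + L] = (1-L)d
- Opposite fills: (1-L)d ± L. For an outcome with range R, the last term is ± L×R.

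With equal loss, then, the two fills give the same difference and cannot reverse its sign. Only the variance changes.

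**10% loss, 343 per arm, design effect 1.2**

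| Fill of missing values | Green | Control | Difference | SE | z | p |
|---|---|---|---|---|---|---|
| all 0 | 7.56% | 14.76% | -7.2 | 2.63 | -2.73 | 0.006 |
| all 1 | 17.56% | 24.76% | -7.2 | 3.42 | -2.11 | 0.035 |
| green 1, control 0 | 17.56% | 14.76% | +2.8 | 3.08 | 0.91 | 0.36 |
| green 0, control 1 | 7.56% | 24.76% | -17.2 | 3.08 | -5.59 | <0.001 |

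The first two rows agree, so the rule accepts the result and multiple imputation is skipped. The last two rows are the true bounds, and they include no effect. At 416 per arm the two common fills give p=0.003 and 0.020, the same wrong pass. At 5% loss and 343 per arm, the common fills give -7.6 points (p=0.005 and 0.015), while the adverse bound is -7.6 + 5.0 = -2.6 points (p=0.37).

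The sign can reverse once (1-L)|d| < L, that is L > |d|/(1+|d|) = 0.08/1.08 = 7.4%.

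**20% loss, same rates**

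Both fills give 0.8 × (-8.0) = -6.4 points; the true bounds are -26.4 to +13.6. Here the check usually works as a trigger:

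- 343 per arm: all-0 p=0.005, all-1 p=0.067, even without the design effect. Multiple imputation is triggered.
- 416 per arm: all-1 p=0.044 without the design effect (a pass), but p=0.066 with it (triggered).

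**Symptom days, 20% loss, assumed 0-14 scale**

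The multi-site asthma study gives 2.62 vs 3.21 days, d = -0.59. The SDs from the stated standard errors are 0.12×√407 = 2.42 and 0.13×√414 = 2.65. Both fills give 0.8 × (-0.59) = -0.47. Without the design effect, all-minimum gives p=0.015 and 0.008 (343 and 416 per arm), and all-maximum gives p=0.21 and 0.17. Multiple imputation is triggered.

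**Unequal loss: 25% green, 15% control (assumed)**

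- All 0: 0.75×8.4 - 0.85×16.4 = 6.30 - 13.94 = -7.6 points.
- All 1: (6.30 + 25) - (13.94 + 15) = +2.4 points.

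The sign changes, so multiple imputation is triggered.

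**The case against.** The strongest reply is that the section is more guarded than a bare reading suggests. It limits the device to small missingness and large effects, says that in general these conditions may fail, and then describes multiple imputation that can allow for non-ignorable missingness. Nothing places the planned 20% loss in the small category. This stands as far as it goes. However, small has no threshold, the operative trigger is whether the inference changes, and the wrong pass above occurs at 10% and 5% loss, where the device is most likely to be used.

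A second reply is that opposite fills by arm are not excluded. That is true. But the literal wording and the worst-endpoint analogy both describe one common value, and nothing points to crossing.

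A third is that the identical difference is a feature of the risk-difference scale, whereas the protocol plans odds or risk ratios. That is also true. In the 10% example the odds ratio is 0.47 with all at 0 and 0.65 with all at 1. Crossed by arm it runs from (0.0756/0.9244)/(0.2476/0.7524) = 0.25 to (0.1756/0.8244)/(0.1476/0.8524) = 1.23. The common fills still miss the bounds.

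Two stronger readings are tempting. A reader might infer that the check nearly always passes because the two differences match. The test is on inference, not on the point estimate, and the larger variance at the maximum triggers multiple imputation in most of the 20% cases above. A reader might also infer that the check conceals unequal dropout. The 25% versus 15% example shows that it can react strongly to that.

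**Conclusion.** The point holds in a limited form. As written, the check can certify a result as robust when it is not, and multiple imputation is then skipped. With the protocol's own exit rates and 10% loss per arm, a difference of -7.2 points passes both fills while the true bounds run from -17.2 to +2.8 points. What the check misses is dropouts whose outcomes differ by arm when loss rates are similar.

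The conclusion rests on reading the rule as one common extreme for all lost subjects, on equal loss, and on a two-sided 0.05 test with design effect 1.2. It concerns binary and bounded asthma outcomes. Allergen, volatile organic compound and pesticide levels have no practical upper bound and already go to multiple imputation under the section's own exception. The change should be made, but the documents do not show that the planned analyses would generally go wrong at the anticipated 20% loss.

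**What to change.** - Make multiple imputation, or a likelihood-based mixed model, the main analysis whatever the bounds show, with site and building in the model.
- Keep bounding as a sensitivity analysis only. Define the extremes as opposite by arm: missing green at worst with missing control at best, and the reverse.
- Delete the rule that filled data are analysed as they stand when the two fills agree.

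The cost is a change of wording, one extra sensitivity run, and a less favourable statement of robustness.

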- Zhang, J., & Yu, K. F. (1998). What's the relative risk? A method of correcting the odds ratio in cohort studies of common outcomes. *Jama*, 280(19), 1690-1691.

Appendix 1

**Instructions for collection of nasal and throat swabs
for assessment of acute respiratory illness**

Green Housing Study

INSTRUCTIONS FOR COLLECTING NASAL AND THROAT SWABS (for Mothers/ Primary Caregivers)

- **Please collect a nasal and throat swab** from your child if he/she has at least 2 of these symptoms for more than 24 hours: fever or feels feverish, stuffy or running nose, cough, sore throat, body aches or tiredness.
- Please collect the nasal swab **as soon as you notice your child has had symptoms for at least 24 hours**, but you may do it up to 7 days from when their symptoms started.
- **Equipment you will need**
 - A clean nasal swabs
 - A clean throat swab
 - A clean tongue depressor
 - A container tube with study label
 - A specimen bag
 - Study labels
- **Before collecting the swab**
 - Gather all equipment
 - Place a study label on the container tube and place a study label on the symptom checklist. Also place the date that you collect the swabs on the checklist paper.
 - Wash your hands with soap and warm water before taking the swab
- **Collecting the swab**
 - With your child seated, tilt their head back gently and keep their head steady by placing a hand on their chin.
 - With the other hand, place the end of a clean swab in the front part of one of their nostrils and gently rub the inner wall. Make sure there is mucous on the swab. If there is no mucous, try getting the sample from that side of the nose again.
 - Remove the swab from the first nostril and place that same swab in the front part of the other nostril and gently rub the inner wall. Again, make sure there is mucous on the swab.
 - Remove the cap from the container tube.
 - Place the swab in the tube and seal the tube lid until it is tight. If the swab does not fit in the container tube, break off the end of the swab with your hand and then seal the lid.
 - Gently tilt the child's head back again. Ask he/she to open their mouth wide. Use the tongue depressor to get a good view of the back of the throat. Rub the swab several times around back of the throat. Place the throat swab in the same tube as the nasal swab. Break off the end of the swab and tightly close the lid.
 - Place the container tube with the swabs in the specimen bag.
- **After getting the swab**
 - Wash your hand using soap and warm water.

- Place the specimen bag with the tube into your refrigerator
- Fill out the symptom check list and please make sure that a study label and the date that you collected the specimen are placed on the checklist paper.
- As soon as you collect the nasal swab, please call the study nurse (XXX-XXX-XXXX) to arrange for pick-up.
- When they pick up the swab, they will also be collecting additional swabs (nasal and throat) on your child, so please make sure your child and an adult will be available during the pick-up time.

**IF YOU HAVE ANY QUESTIONS OR PROBLEMS, PLEASE CALL YOUR STUDY COORDINATOR
AT
XXX-XXX-XXXX**

Green Housing Study

INSTRUCTIONS FOR COLLECTING NASAL AND THROAT SWABS (for Study Technicians)

- **When you will be contacted**
 - Mothers/ primary caregivers have been instructed to collect nasal and throat swabs when their child has at least 2 of the following symptoms for more than 24 hours: fever or feels feverish, stuffy or running nose, cough, sore throat, body aches or tiredness.
 - Please arrange to pick up the specimen as soon as possible after the specimen has been collected. Please make sure the child and an adult will be available during the pick-up time, since you will be collecting additional specimens.
- **Equipment you will need**
 - Nasal and throat swabs
 - Collection tube
 - Tube holder
 - Tongue depressor
 - Specimen bag
 - Cooler with cold ice packs
 - Gloves
 - Study labels
- **Before collecting the swabs**
 - Gather all equipment
 - Label the collection tube with the study label and collection date.
 - Wash your hands with soap and warm water. Place gloves over clean, dry hands.

- **Collecting the swabs**
 - With the child seated, tilt their head back gently and place one hand on their chin to steady their head.
 - With the other hand, place the end of a clean nasal swab in the front part of one of their nostrils and gently rub the inner wall. Make sure there is mucous on the swab. If there is no mucous, try getting the sample from that side of the nose again.
 - Remove the swab from the first nostril and place that same swab in the front part of the other nostril and gently rub the inner wall. Again, make sure there is mucous on the swab.
 - Place the nasal swab in the transport medium tube being careful to avoid touching the sides or rim of the tube and close the lid after breaking the end of the swab off. Place the tube in the tube holder.
 - Gently tilt the child's head back again. Ask he/she to open their mouth wide. Use the tongue depressor to get a good view of the posterior pharynx and tonsils (back of the throat). Rub the swab several times around the posterior pharynx and tonsils (back of the throat). Place the oral swab in the same transport medium as the nasal swab being careful to avoid touching the sides or rim of the tube. Break off the end of the swab and tightly close the lid.
- **After collecting the swab**
 - Place the viral transport tube in a specimen bag and place it in the cooler.
 - Remove your gloves and wash your hands with soap and warm water.
 - Obtain the parent collected nasal swab specimen from the family's refrigerator and place it in the cooler. Make sure the tube is labeled and also collect the symptom checklist from the parent.
- **Storage of specimens**
 - When you arrive at the storage laboratory, please check to make sure all the tubes are properly labeled and logged into the study log book. Please store them in -70 C until shipped to CDC.

**IF YOU HAVE ANY QUESTIONS OR PROBLEMS, PLEASE CALL THE STUDY COORDINATOR
AT XXX-XXX-XXXX.**
